5.1 Description

Ca-DTPA (Pentetate calcium trisodium injection 1g/5 mL) and

Zn-DTPA (Pentetate zinc trisodium injection 1 g/5 mL).

5.2 Treatment Regimen

Initially, 2.5 mL of Ca-DTPA (1 g/5 ml) will be administered over a period of 1 minute. A solution of normal saline will then be administered at a rate of 300 mL/hr over 30 minutes. The patient will be seated with hands lowered to their sides to allow the chelator to dwell slightly in the soft tissues of the hands and feet. The patient will then be moved to a supine position and the infusion rate will then be increased to 750 mL/hr over the next 60 minutes. At 90 minutes the remaining 2.5 mL of Ca-DTPA will administered I.V. over a period of 1 minute, and the normal saline will continue for the remaining 9 minutes. The I.V. line will then be removed. The patient will be instructed to drink plenty of fluids that evening. The following day, the treatment will be repeated using Zn-DTPA. The same treatment therapy will consist of 3 time-points, approximately 1 month apart.

5.3 Method for Assigning Subjects to Treatment Groups

No randomization will be used. All patient subjects will receive the same treatment therapy.

5.4 Preparation and Administration of Study Drug

The appropriate doses will be drawn into a syringe from the Ca-DTPA and Zn-DTPA ampoules by the trained nursing staff and administered intravenously by a physician through an IV infusion line with the agents administered through a T-valve connection as a bolus. No placebo will be used.

5.5 Subject Compliance Monitoring

Subjects are treated and discharged from the clinic. They will be instructed to drink plenty of fluids, and collect urine for the following 24 hours to be returned the following day. Subjects will also have blood chemistries drawn the day following the second infusion for monitoring. Subject treatment will discontinue if they do not collect the 24 hour urine sample for testing following the infusion therapy, or refuse blood chemistry monitoring.

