4.4 Early Withdrawal of Subjects

Patients may remove themselves from the study at any time for any reason. The investigators may remove patients from the study for any reason, such as non-compliance, or patient safety concerns.

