4.4.1 When and How to Withdraw Subjects

Study subjects will be withdrawn from the study if they experience any known or unknown severe adverse event following administration of either Ca-DTPA or Zn-DTPA. Treatment will be discontinued immediately following any severe adverse event.

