6.3 **Visit 2-** The patient subject will come for the second infusion therapy with Zn-DTPA. Patient will void and have a baseline blood pressure taken prior to initiation of therapy. Blood samples will be collected by phlebotomy trained staff at the Clinical & Translational Research Center (CTRC) at UNC Memorial hospital. Patient blood samples will be obtained just prior to intravenous administration of Ca-DTPA or Zn-DTPA. IV placement will be done by nursing staff, normal saline infusion started, and Zn-DTPA injections will be done by investigator or one of the co-investigators exactly as the day prior. Five (5) minutes post injection of Zn-DTPA another blood pressure will be taken. Another 24-hour urine sample will be collected beginning after chelation therapy is initiated, to be returned then next day.

6.4 **Visit 3-** The patient will return to the hospital to drop off 24 hour urine for gadolinium testing, as well as a creatinine clearance. Blood chemistries calcium, zinc, magnesium and manganese will be evaluated, along with BUN, creatinine, sodium, potassium, chloride, phosphorus and CO₂.

6.5 **Visit 4-** The patient subject will come for a follow up assessment by a clinician 1 week (+5 days) following IV therapy, where pain and overall health assessments will be performed. If the patient lives more than 3 hours away, a phone-call follow up will be done and questionnaires will be supplied to be filled out and emailed prior to leaving the infusion therapy. The second therapy session will be scheduled for the following month.

6.6. **Visit 5-** Patient will return for 2nd round of infusion therapy to be done exactly as first, with day one of Ca-DTPA including pregnancy testing on women of child-bearing potential and pain scale assessment sheets for the week. Blood samples will be collected by phlebotomy trained staff at the Clinical & Translational Research Center (CTRC) at UNC Memorial hospital. Patient blood samples will be obtained just prior to intravenous administration of Ca-DTPA or Zn-DTPA.

6.7 **Visit 6-** Patient returns for day two of infusion therapy with Zn-DTPA. Blood samples will be collected by phlebotomy trained staff at the Clinical & Translational Research Center (CTRC) at UNC Memorial hospital. Patient blood samples will be obtained just prior to intravenous administration of Ca-DTPA or Zn-DTPA

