6.8 **Visit 7-** The patient will return to the hospital to drop off 24-hour urine for gadolinium testing, as well as a creatinine clearance. Blood chemistries calcium, zinc, magnesium and manganese will be evaluated, along with BUN, creatinine, sodium, potassium, chloride, phosphorus and CO₂.

6.9 **Visit 8-** One week post treatment follow up visit for health assessments as before. Third therapy session will be scheduled for one month out.

6.10 **Visit 9-** Patient returns for final round of infusion therapy to be done exactly as first two treatments with day one of Ca-DTPA, including pregnancy testing on women of child-bearing potential and pain assessment sheets for the week. Blood samples will be collected by phlebotomy trained staff at the Clinical & Translational Research Center (CTRC) at UNC Memorial hospital. Patient blood samples will be obtained just prior to intravenous administration of Ca-DTPA or Zn-DTPA

6.11 **Visit 10-** Patient returns for day two of infusion therapy with Zn-DTPA. Blood samples will be collected by phlebotomy trained staff at the Clinical & Translational Research Center (CTRC) at UNC Memorial hospital. Patient blood samples will be obtained just prior to intravenous administration of Ca-DTPA or Zn-DTPA

6.12 **Visit 11-** The patient will return to the hospital to drop off 24-hour urine for gadolinium testing, as well as a creatinine clearance. Blood chemistries calcium, zinc, magnesium and manganese will be evaluated, along with BUN, creatinine, sodium, potassium, chloride, phosphorus and CO₂.

6.13 **Visit 12-** Subject returns for final follow up assessments 1 week (+5 days) following last infusion therapy. If patient lives more than 3 hours away, a phone-call will be done by the treating physician or clinician.

6.14 **Visits 13-14-** Subjects will receive a phone call from the coordinator to go over pain the pain assessment scale at months 6 and 12 following treatment.

At any time in between treatments if the clinician or patient feels they need to be seen, they will be brought in to the clinic (or to their local healthcare provider) for evaluation and possible discontinuation of therapy.

7 Statistical Plan

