8.2 Recording of Adverse Events

At each contact with the subject, the investigator must seek information on adverse events by specific questioning and, as appropriate, by examination. Information on all adverse events should be recorded immediately in the source document, and also in the appropriate adverse event module of the case report form (CRF). All clearly related signs, symptoms, and abnormal diagnostic procedures results should be recorded in the source document, though should be grouped under one diagnosis.

All adverse events occurring during the study period must be recorded. The clinical course of each event should be followed until resolution, stabilization, or until it has been determined that the study treatment or participation is not the cause. Serious adverse events that are still ongoing at the end of the study period must be followed up to determine the final outcome. Any serious adverse event that occurs after the study period and is considered to be possibly related to the study treatment or study participation should be recorded and reported immediately.

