12.2 Conflict of Interest

Any investigator who has a conflict of interest with this study (patent ownership, royalties, or financial gain greater than the minimum allowable by their institution, etc.) must have the conflict reviewed by a properly constituted Conflict of Interest Committee with a Committee-sanctioned conflict management plan that has been reviewed and approved by the study sponsor prior to participation in this study. All University of UNC investigators will follow the University conflict of interest policy.

13 Publication Plan

Neither the complete nor any part of the results of the study carried out under this protocol, nor any of the information provided by the sponsor for the purposes of performing the study, will be published or passed on to any third party without the consent of the study sponsor. Any investigator involved with this study is obligated to provide the sponsor with complete test results and all data derived from the study.

14 References

1. Sieber MA1, Lengsfeld P, Walter J, Schirmer H, Frenzel T, Siegmund F, Weinmann HJ, Pietsch H., Gadolinium-based contrast agents and their potential role in the pathogenesis of nephrogenic systemic fibrosis: the role of excess ligand. *J Magn Reson Imaging*. 2008 May;27(5):955-62 doi: 10.1002/jmri.21368

15 Appendices

- A. Table of Events
- B. Visual Analog Pain Scale
- C. Quality of Life scale
- D. Copy of Consent Form

Time and Events Table:

	Pre-treatment Visit 0	V 1 Day 1	V 2 Day 2	V 3 Day 3	V 4 Day 7	V 5 Day 1 Mo 2	V 6 Day 2 Mo 2	V 7 Day 3 Mo 2	V 8 Day 7 Mo 2	V 9 Day 1 Mo 3	V10 Day 2 Mo 3	V 11 Day 3 Mo 3	V 12 Day 7 Mo 3	V 13-14 Mo 6 & 12
Physical Assessments	X				X				X				X	
Labs	X	X ^c		X		X ^c		X		X ^c		X		
24 hr urine gd	X	X ^a	X ^a			X ^a	X ^a			X ^a	X ^a			
Pain/QOL questionnaire	X				X ^e				X ^e				X ^e	X ^d
IV Ca-DTPA therapy		X				X				X				
IV Zn-DTPA therapy			X				X				X			

- a. Patients will begin 24hr urine collection immediately following therapy
- b. Assessments may be done by phone when patient lives greater than 3 hours away
- c. Urine pregnancy testing will be done on day one of therapy for WCBP

- d. Patients will be called to collect pain and QOL data at months 6 and 12
- e. Pain/QOL questionnaires will be filled out days 1-6 and returned day 7

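### No calcium is named between Ca-DTPA and Zn-DTPA in any of the 3 rounds, so the 8.4 hypocalcemia rule has no named current-round value when Zn-DTPA is given

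*Combined protocol and SAP*

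**What the plan says.** Section 3.4 makes hypocalcemia the sole primary safety endpoint and gives no time point. Section 8.4 removes from the study a patient whose calcium is Grade 3 (under 7.0, down to 6.0 mg/dl) after infusion therapy. Section 4.4.1 applies withdrawal to severe events "following administration of either Ca-DTPA or Zn-DTPA. Treatment will be discontinued immediately following any severe adverse event".

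Treatment is 3 monthly rounds, each with 1 g Ca-DTPA on day 1 (V1, V5, V9) and 1 g Zn-DTPA on day 2 (V2, V6, V10).

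The protocol describes blood sampling in these places:

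- **Screening (4.3):** a chemistry panel that includes calcium.
- **Monitoring (5.5):** "Subjects will also have blood chemistries drawn the day following the second infusion for monitoring".
- **V3, V7 and V11 (6.4, 6.8, 6.12):** "Blood chemistries calcium, zinc, magnesium and manganese will be evaluated", with other chemistries.
- **Dosing days, including V2, V6 and V10 (6.3, 6.7, 6.11):** "Patient blood samples will be obtained just prior to intravenous administration of Ca-DTPA or Zn-DTPA". No analyte is given.
- **Research blood (3.1):** two 6 mL heparin tubes, one for flow cytometry and one for cytokines and chemokines. They are not assigned to visits.
- **Time and Events Table:** Labs is marked at V0, V1, V3, V5, V7, V9 and V11 and is blank at V2, V6 and V10. The V1, V5 and V9 marks carry footnote c: "Urine pregnancy testing will be done on day one of therapy for WCBP". What else those marks cover is not stated.

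**The concern.** The plan singles out one laboratory abnormality as its safety endpoint and attaches a discontinuation rule to it. The first named calcium of each round nevertheless comes after the second agent. A patient whose calcium has fallen by day 2, without recognised symptoms or signs, would be given Zn-DTPA under the written schedule.

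Two things are at stake. The sponsor's own rule acts later than it needs to. And a fall first seen on day 3 follows both agents, so the data say little about which one caused it. Section 7.1 says the 20 subjects are there to establish the safety profile of chelation, and section 8.1 lists different expected adverse events for Ca-DTPA and Zn-DTPA.

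**Working it through.** The plan states no figure on this point to reproduce. The check is a count of scheduled draws, followed by simple arithmetic.

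**Step 1. Named calcium by round** (5.5, 6.2 to 6.12, Time and Events Table)

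| Round | Ca-DTPA (day 1) | Zn-DTPA (day 2) | Named calcium between the two | First named calcium after dosing |
|---|---|---|---|---|
| 1 | V1 | V2 | 0 | V3, day 3 |
| 2 | V5 | V6 | 0 | V7, day 3 |
| 3 | V9 | V10 | 0 | V11, day 3 |

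The total after Ca-DTPA alone is 0 of 3. The total after both agents is 3 of 3.

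**Step 2. Could the pre-Zn-DTPA draw already carry calcium?** It could, because its contents are unspecified. But the protocol lists analytes where it wants chemistries (screening, V3, V7, V11) and lists none here. The only other blood uses it describes are the research assays in 3.1. The blank Labs cells point the same way, but only as support, since that row does not record every draw. Even if a calcium were run, nothing makes Zn-DTPA depend on the result.

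**Step 3. Dose given before the first named value.** 1 g + 1 g = 2 g, with the value on day 3. With calcium added to the day-2 draw, it is 1 g, with the value on day 2.

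**Step 4. Where the rule does work.** There are 3 × 2 = 6 infusions per subject. A V3 or V7 value precedes V5, V6, V9 and V10, which is 4 of 6.

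**Step 5. Age of the latest calcium when Zn-DTPA is given.** In every case it predates that round's Ca-DTPA.

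- If the day-1 Labs marks include chemistries: 2 − 1 = 1 day.
- If not, round 1: screening up to 7 days before day 1 (6.1), plus 1 = up to 8 days.
- If not, rounds 2 and 3: taking a month as 28 to 31 days (assumption), Zn-DTPA falls on day 30 to 33 counted from the previous round's day 1. 30 − 3 = 27 and 33 − 3 = 30, so 27 to 30 days.
- As the last case, for patients living more than 3 hours away whose local labs (day 7 to 14) include calcium (assumption): 30 − 14 = 16 to 33 − 7 = 26 days.

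The overall range is 1 to 30 days. Its width reflects unstated lab contents; it does not measure the size of the problem.

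**Step 6. Other routes to a calcium value.** The screening panel is repeated for withdrawn subjects (4.4.2), and unscheduled visits are allowed. Neither is a scheduled measurement for a subject who is continuing.

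**The case against.** The strongest reply has four parts.

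*The draw exists.* A reader might infer that calcium is never measured after Ca-DTPA alone. The documents do not support that: they show a draw with unspecified contents, not one that excludes calcium. This stands, and the point is confined to what is named and required.

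*The rule can be applied as written.* A reader might infer that the 8.4 rule is inoperative. It is not: V3 and V7 inform the following rounds. Infusion therapy in 8.4 can also be read as the whole two-day round, in which case a day-3 value serves it. Section 4.4.1 leans towards a per-agent reading, since it covers either agent and stops treatment at once, but it sets no laboratory timing. The ambiguity stands.

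*Risk looks low and other safeguards exist.* Section 1.4 reports 3077 doses in 485 patients, with minor transient effects in 12 and nothing serious or long-term. Calcium has the lowest binding constant in the section 1.3 table (log K 10.74). Hypocalcemia is not among the expected adverse events in 8.1. Patients with symptoms can be caught by 8.2 ("At each contact with the subject, the investigator must seek information on adverse events by specific questioning"), by 4.4 ("The investigators may remove patients from the study for any reason, such as non-compliance, or patient safety concerns") and by unscheduled evaluation at the end of section 6 ("At any time in between treatments if the clinician or patient feels they need to be seen"). All of this stands and limits the consequence. It does not reach the patient with low calcium and no symptoms, for whom a laboratory rule is needed.

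*The fix is partial.* Section 7.1 asks about chelation as a whole, not each agent. With a day-2 value, a further fall on day 3 could still be a late Ca-DTPA effect, a Zn-DTPA effect or both. A brief early fall could be missed on day 2 as on day 3. This also stands: attribution would improve but not be settled.

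**Conclusion.** The point holds in a limited form. In 0 of 3 rounds does the written schedule name a calcium between the two agents or make Zn-DTPA depend on one. The 8.4 rule therefore has no named value reflecting the current round's Ca-DTPA when Zn-DTPA is given. For a patient without symptoms, discontinuation comes about a day, and 1 g of DTPA, later than it could. The ability to separate the agents' effects on calcium is also reduced.

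A reader might infer that giving Zn-DTPA to a hypocalcemic patient does further harm. The documents give no calcium time course, no frequency of Grade 3 hypocalcemia and no evidence that Zn-DTPA worsens it, so no added harm is shown.

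The conclusion assumes that the unspecified pre-Zn-DTPA draw carries no calcium with a result required before dosing. If the sponsor already intends one, the amendment records it and adds the hold. The change is worth making because it is cheap and serves the plan's only primary safety endpoint.

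**What to change.** In 6.3, 6.7 and 6.11, name calcium as an analyte of the existing pre-Zn-DTPA draw, taken on arrival when the day-1 urine is handed in. Mark Labs at V2, V6 and V10 in the Time and Events Table. State that Zn-DTPA is withheld if the result meets the 8.4 threshold. Keep the V3, V7 and V11 calcium, so that each round has one value after Ca-DTPA alone and one after both agents.

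The cost is at most 20 × 3 = 60 extra calcium assays, possibly one extra tube at a venepuncture already planned, and a wait on day 2. The documents give no turnaround time. At an assumed 0.5 to 2 hours per result, the wait totals 60 × 0.5 = 30 to 60 × 2 = 120 patient-hours over the study.

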5.6 Prior and Concomitant Therapy

We will be excluding patients who have had an investigational product administered within the previous 30 days.

5.7 Packaging

The study drug will be used as supplied by the manufacturer. Vials will be received from the manufacturer packaged as 10 ampoules (1g/5 mL) Ca-DTPA and 10 ampoules (1gm/5 mL) of Zn-DTPA. A total of four packages (40 ampoules) of each product will be received. This will allow enough doses for each subject to be administered up to three doses of Ca-DTPA and three doses of Zn-DTPA as well as allowing extra vials for breakage, spillage, etc.

5.8 Blinding of Study Drug (if applicable)

No blinding of drug will be incorporated. All patient subjects will be treated with the same therapy regimen.

5.9 Receiving, Storage, Dispensing and Return

5.9.1 Receipt of Drug Supplies

Study drug receipt, storage, and dispensing and accountability will be managed by our Investigational Drug Services pharmacy. Upon receipt of the of the study treatment supplies, an inventory is performed and a drug receipt log filled out and signed by the person accepting the shipment. The investigator must notify study sponsor of any damaged or unusable study treatments that were supplied to the investigator's site.

5.9.2 Storage

The manufacturer recommends that the products be stored between 15 - 30°C (59 - 86°F), and will be stored in the Investigation Drug pharmacy.

5.9.3 Dispensing of Study Drug

Study drug receipt, storage, and dispensing and accountability will be managed by our Investigational Drug Services pharmacy. The pharmacy must notify study sponsor of any damaged or unusable study treatments that were supplied to the investigator's site. Regular study drug reconciliation will be performed to document drug assigned and when.

5.9.4 Return or Destruction of Study Drug

At the completion of the study, there will be a final reconciliation of drug shipped, drug consumed, and drug remaining. This reconciliation will be logged on the drug reconciliation form, signed and dated. Any discrepancies noted will be investigated, resolved, and documented prior to return or destruction of unused study drug. Drug destroyed on site will be documented in the study files.

6 Study Procedures

6.1 **Visit 0-** The patient will be seen and evaluated by a UNC clinician regarding symptoms, assessments, a physical exam, a medication history and lab values up to one week prior to anticipated therapy start date. After agreeing to participate in the study, a coordinator will obtain informed consent signatures and the patient will be instructed to collect a 24-hour urine so that gadolinium can be measured for pre-treatment values.

6.2 **Visit 1-** The patient will come for infusion chelation therapy with Ca-DTPA to be done in the Clinical and Translational Research Center. Patient will void and have a baseline blood pressure taken before start of treatment. A urine pregnancy test will be performed if the subject is a woman of child-bearing potential. Blood samples will be collected by phlebotomy trained staff at the Clinical & Translational Research Center (CTRC) at UNC Memorial hospital. Patient blood samples will be obtained just prior to intravenous administration of Ca-DTPA or Zn-DTPA. The IV will be placed by nursing staff, and the infusion of normal saline will begin. The first injection of Ca-DTPA is performed by the investigator, or one of the co-investigators. Five (5) minutes post injection of Ca-DTPA another blood

pressure will be taken. Saline will continue for another 80 minutes, and the second injection of Ca-DTPA will be given by an investigator, followed by the last 10 minutes of saline infusion. IV will be discontinued, vitals checked, and patient will be discharged home. Patient will begin 24-hour urine collection once the infusion is started. They will be instructed to drink plenty of fluids. Analog pain scale sheets will be given to the subject to fill out starting with day 1 through day 6 post treatment, which will be returned on the day 7 visit. Urine is to be brought in on 2nd day of therapy.

6.3 **Visit 2-** The patient subject will come for the second infusion therapy with Zn-DTPA. Patient will void and have a baseline blood pressure taken prior to initiation of therapy. Blood samples will be collected by phlebotomy trained staff at the Clinical & Translational Research Center (CTRC) at UNC Memorial hospital. Patient blood samples will be obtained just prior to intravenous administration of Ca-DTPA or Zn-DTPA. IV placement will be done by nursing staff, normal saline infusion started, and Zn-DTPA injections will be done by investigator or one of the co-investigators exactly as the day prior. Five (5) minutes post injection of Zn-DTPA another blood pressure will be taken. Another 24-hour urine sample will be collected beginning after chelation therapy is initiated, to be returned then next day.

6.4 **Visit 3-** The patient will return to the hospital to drop off 24 hour urine for gadolinium testing, as well as a creatinine clearance. Blood chemistries calcium, zinc, magnesium and manganese will be evaluated, along with BUN, creatinine, sodium, potassium, chloride, phosphorus and CO₂.

6.5 **Visit 4-** The patient subject will come for a follow up assessment by a clinician 1 week (+5 days) following IV therapy, where pain and overall health assessments will be performed. If the patient lives more than 3 hours away, a phone-call follow up will be done and questionnaires will be supplied to be filled out and emailed prior to leaving the infusion therapy. The second therapy session will be scheduled for the following month.

6.6. **Visit 5-** Patient will return for 2nd round of infusion therapy to be done exactly as first, with day one of Ca-DTPA including pregnancy testing on women of child-bearing potential and pain scale assessment sheets for the week. Blood samples will be collected by phlebotomy trained staff at the Clinical & Translational Research Center (CTRC) at UNC Memorial hospital. Patient blood samples will be obtained just prior to intravenous administration of Ca-DTPA or Zn-DTPA.

6.7 **Visit 6-** Patient returns for day two of infusion therapy with Zn-DTPA. Blood samples will be collected by phlebotomy trained staff at the Clinical & Translational Research Center (CTRC) at UNC Memorial hospital. Patient blood samples will be obtained just prior to intravenous administration of Ca-DTPA or Zn-DTPA

6.8 **Visit 7-** The patient will return to the hospital to drop off 24-hour urine for gadolinium testing, as well as a creatinine clearance. Blood chemistries calcium, zinc, magnesium and manganese will be evaluated, along with BUN, creatinine, sodium, potassium, chloride, phosphorus and CO₂.

6.9 **Visit 8-** One week post treatment follow up visit for health assessments as before. Third therapy session will be scheduled for one month out.

6.10 **Visit 9-** Patient returns for final round of infusion therapy to be done exactly as first two treatments with day one of Ca-DTPA, including pregnancy testing on women of child-bearing potential and pain assessment sheets for the week. Blood samples will be collected by phlebotomy trained staff at the Clinical & Translational Research Center (CTRC) at UNC Memorial hospital. Patient blood samples will be obtained just prior to intravenous administration of Ca-DTPA or Zn-DTPA

6.11 **Visit 10-** Patient returns for day two of infusion therapy with Zn-DTPA. Blood samples will be collected by phlebotomy trained staff at the Clinical & Translational Research Center (CTRC) at UNC Memorial hospital. Patient blood samples will be obtained just prior to intravenous administration of Ca-DTPA or Zn-DTPA

6.12 **Visit 11-** The patient will return to the hospital to drop off 24-hour urine for gadolinium testing, as well as a creatinine clearance. Blood chemistries calcium, zinc, magnesium and manganese will be evaluated, along with BUN, creatinine, sodium, potassium, chloride, phosphorus and CO₂.

6.13 **Visit 12-** Subject returns for final follow up assessments 1 week (+5 days) following last infusion therapy. If patient lives more than 3 hours away, a phone-call will be done by the treating physician or clinician.

6.14 **Visits 13-14-** Subjects will receive a phone call from the coordinator to go over pain the pain assessment scale at months 6 and 12 following treatment.

At any time in between treatments if the clinician or patient feels they need to be seen, they will be brought in to the clinic (or to their local healthcare provider) for evaluation and possible discontinuation of therapy.

7 Statistical Plan

